13.1.1.3. Treatment-Emergent Adverse Event

A treatment-emergent AE (TEAE) is any event not present before the initiation of the investigational product or any event already present that worsens in either intensity or frequency following exposure to the investigational product.

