8.4. Dose Adjustment, Interruption, and Withdrawal from Investigational Product or Study

Investigational product may be temporarily decreased (eg, from 10 mg twice weekly to 5 mg twice weekly, or from 5 mg twice weekly to 5 mg once weekly) or temporarily or permanently stopped based on tolerability concerns. Investigational product may be resumed at the maintenance dose upon resolution of gastroenteritis or worsening renal function or dehydration if there is no evidence of liver injury. For rechallenge following all other dose interruptions (see Table 5), investigational product should be initiated at a lower dose and patients monitored more frequently with up-titration considered based on tolerability.

Adjustments, interruptions, discontinuation, and any rechallenge of investigational product should be implemented per the criteria outlined in Table 5. Patients that discontinue investigational product are expected to continue in the study (and follow the regular visit schedule, with the exception of PK sampling [trough PK may be required in the event of an AE consistent with hepatic injury or decompensation]) until the end of the study, but may withdraw consent at any time.

Table 5: Criteria for Dose Adjustment, Interruption, Discontinuation, and Rechallenge

DOSE ADJUSTMENT		
Criteria	Action Taken with IP	Adjustment
New Onset Severe Pruritus	Drug holiday or less frequent dosing	Return to original dose regimen if tolerated
DOSE INTERRUPTION		
Criteria	Action Taken with IP^a	Rechallenge^b
If liver biochemistries indicative of suspected hepatic injury are identified as exceeding upper threshold criteria and require immediate interruption (see Part A of Table 3) ^c	Interrupt immediately upon initial observation	Patient may be rechallenged after a minimum of 30 days if fully resolved OR stable and approved by the Medical Monitor and Investigator.
Other liver biochemistries indicative of suspected hepatic injury are outside upper threshold criteria upon repeat testing as defined in Part A of Table 3 ^d	Interrupt after confirmation by repeat testing	
Liver biochemistries indicative of potential hepatic decompensation in the absence of symptoms (see Part B of Table 3) ^e	Closely monitor until normalization or stabilization. If values continue to increase relative to the baseline value, interrupt	

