8.4.1. Other Reasons for Discontinuation of Study or Investigational Product

The following events are considered appropriate reasons for a patient to discontinue investigational product; however, these patients are expected to continue in the study until study termination (or at the discretion of the Sponsor):

- Patient begins treatment with commercially available OCA.
- The Investigator or Sponsor considers that it is advisable or in the best interest of the patient.
- The occurrence of clinical or laboratory AEs considered by the Investigator to be clinically important safety concerns and related to study drug.
- Withdrawal of consent
 - Consent may be fully withdrawn (in which case the patient discontinues both investigational product and study visits and procedures).
 - Consent may be modified to discontinue study visits but allow semi-annual telephone contact.

- Consent may be modified to discontinue study visits or semi-annual telephone contact but allow continued access to medical records to assess for suspected major adverse cardiovascular events (MACE) and liver-related clinical events.
- Early termination procedures should be conducted if the patient withdraws consent (see [Section 9.7.13](#)).

The Investigator is encouraged to contact the Sponsor prior to discontinuing a patient from treatment. The Investigator must notify the Sponsor study monitor by telephone or email as soon as possible if any patient prematurely withdraws from the study.

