9.2.2. Prohibited Medications

Commercial OCA therapy (if available) is prohibited while on investigational product, and if prescribed during the course of the study, the Investigator should be cognizant of the possibility of double dosing. Patients who initiate with commercial OCA therapy must discontinue investigational product and are expected to continue through the end of the study (see [Section 8.4.1](#)).

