13.1.4. Reporting of Adverse Events and Serious Adverse Events

13.1.4.1. Reporting of Adverse Events

AE data will be collected from the time that signed informed consent is obtained until the patient fully completes her/his study participation.

All AEs, whether believed by the Investigator to be related or unrelated to the investigational product, must be documented in the patient's medical records, in accordance with the Investigator's normal clinical practice and on the AE eCRF. Each AE is to be evaluated for duration, intensity, frequency, seriousness, outcome, other actions taken, and relationship to the investigational product. Redacted medical record source documentation will be requested for all SAEs and emergency room visits.

In addition, the Investigator should contact the study Medical Monitor upon awareness when any signs or symptoms of hepatic decompensation are observed in any patient.

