13.1.6. Notification of Post-Treatment SAEs for Patients Who Continue in the Study

Post-treatment SAEs that occur in patients who remain in the study after investigational product has been discontinued must be reported to the Sponsor within 24 hours by following the instructions provided in [Section 13.1.4.2](#).

SAEs that occur in patients who discontinue investigational product, initiate treatment with commercially available Ocaliva, and remain in the study must be reported to the Sponsor within 24 hours by following the instructions provided in [Section 13.1.4.2](#).

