15.4.4. Adverse Events of Special Interest

Pruritus: Treatment-emergent pruritus, defined as any PT including “Prur,” will be summarized separately by the MedDRA SOC, treatment group, and PT as a subset of all TEAEs. This summary will be repeated for patients with “new or worsened” pruritus events, as defined as follows:

- Mild, moderate, or severe treatment-emergent pruritus events in patients with no pruritus at Baseline, or
- Worsening of the severity of the Baseline condition in patients with pruritus at Baseline.

Baseline pruritus is defined as the Investigator’s rating of severity as collected on the PBC Disease History eCRF. Patients whose Baseline severity is severe will be counted as worsening if an AE of pruritus with severe is recorded.

An analysis of treatment-emergent pruritus event days per patient years on study will be performed. The days at each severity grade, including the total days of event, the total patient years on study, and the event days per patient year on study at each severity grade, including the total, will be summarized. Each individual patient year on study will be derived as the last known date during the study minus the first dose date plus 1 divided by 365.25 days/year.

In order to explore the relationship between pruritus and the investigational product, the following time-to-event analyses will be performed:

- Time to first onset of treatment-emergent pruritus
 - The time to the start of the first episode will be calculated by date of onset of first episode – date of first dose of investigational product + 1.
 - Patients who never reported an AE of pruritus will be censored at the date of last contact.
- Time to onset of the first moderate or severe treatment-emergent pruritus
 - The time to the start of the first moderate or severe pruritus will be calculated by date of onset of the first moderate or severe pruritus – date of first dose of investigational product +1.
 - Patients who never reported a moderate or severe AE of pruritus will be censored at the date of completion or discontinuation.
- Time to onset of the first severe treatment-emergent pruritus
 - The time to the start of the first severe pruritus will be calculated by date of onset of the first severe pruritus – date of first dose of investigational product +1.
 - Patients who never reported a severe AE of pruritus will be censored at the date of completion or discontinuation.

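### Treatment-emergent events have no end date and pruritus and fatigue rates use all study time, with no on-treatment counterpart

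*Protocol*

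**What the plan says.** The protocol fixes five things that act together.

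- **Definition.** Section 13.1.1.3 counts as treatment-emergent "any event not present before the initiation of the investigational product or any event already present that worsens in either intensity or frequency" after exposure to study drug. It gives no closing date.
- **Collection.** Section 13.1.4.1: "AE data will be collected from the time that signed informed consent is obtained until the patient fully completes her/his study participation". Collection ends with participation, not with treatment.
- **Retention.** Section 8.4: "Patients that discontinue investigational product are expected to continue in the study". Section 8.4.1 lists "Patient begins treatment with commercially available OCA" among the reasons to stop study drug while staying in the study. Section 9.2.2 adds: "Patients who initiate with commercial OCA therapy must discontinue investigational product and are expected to continue through the end of the study". Table 6 in Section 9.7.13 places these patients on the regular visit schedule.
- **Tabulation.** The Safety Population (Section 15.1) is everyone dosed. Sections 15.4 and 15.4.1 tabulate events by treatment group without restricting them to time on drug. Section 9.1 limits investigational product to study-supplied OCA or placebo, so starting commercial OCA does not move a placebo patient into the OCA column.
- **Rates and censoring.** Section 15.4.4 sets the denominator for pruritus event-days, converted from days to years: "Each individual patient year on study will be derived as the last known date during the study minus the first dose date plus 1". Fatigue uses the same formula. A patient with no pruritus is censored at last contact, but for the moderate-or-severe endpoint the rule is: "Patients who never reported a moderate or severe AE of pruritus will be censored at the date of completion or discontinuation". First severe pruritus follows that second rule. All three fatigue endpoints use last contact.

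**The concern.** Safety and tolerability against placebo is a primary objective (Section 6.1). No formal safety test is planned (Section 15.4), so the descriptive tables and rates are themselves the result.

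Read as written, new pruritus in a placebo patient who has moved to commercial OCA is a placebo treatment-emergent event. A patient who stops OCA because of itch keeps adding drug-free time to the OCA denominator. This is foreseeable here. OCA is already marketed in the US, Canada and the EU (Section 5.1), pruritus is the main event attributed to it (Section 5.6), and follow-up can reach about 3 years (Section 7.1.3). Section 13.1.6 anticipates the situation by naming "SAEs that occur in patients who discontinue investigational product, initiate treatment with commercially available Ocaliva, and remain in the study", but only as a reporting duty; Section 15.4 does not carry the distinction into the analysis.

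**Working it through.** The protocol states no safety rate, so there is no planned figure to reproduce. The check sizes the effect of the stated rule on the pruritus and fatigue rates.

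**Inputs.** About 50 patients at 1:1 (Section 15.2) gives 25 per arm. The same section assumes 15% discontinuation: 0.15 × 25 = 3.75, about 4 patients. The timing of stopping, the uptake of commercial OCA and the true rate ratio are not in the document and are assumed.

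**Step 1: OCA-arm dilution, no commercial OCA.** If off-drug time carries no event-days, the study-time rate divided by the on-treatment rate is 1 − (off-drug patient-weeks ÷ all patient-weeks).

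- Four of 25 stop at Week 24 and all are followed for 48 weeks: 4 × 24 = 96 of 25 × 48 = 1200 patient-weeks. 1 − 96/1200 = 0.92, a fall of 8%.
- The same four stop at Week 24 and all are followed for 128 weeks (104 off drug): 4 × 104 = 416 of 25 × 128 = 3200. 1 − 416/3200 = 0.87, a fall of 13%.

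**Step 2: rate ratio, allowing background events and commercial OCA.** Assume the same constant hazard of stopping in both arms, h = −ln(1 − d)/48 per week, where d is the proportion stopped by Week 48. The off-drug share of study time over T weeks is s = 1 − (1 − e^(−hT))/(hT). With d = 0.15, s is 7.7% at 48 weeks and 22.3% at 156 weeks.

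Let R be the true on-drug rate ratio and c the share of off-drug time spent on commercial OCA, the same in both arms. Events follow current exposure.

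- OCA arm: (1 − s)R + s[(1 − c) + cR]
- Placebo arm: (1 − s) + s[(1 − c) + cR]

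| R | d | T (weeks) | Ratio, c = 0 | Ratio, c = 0.5 | Ratio, c = 1 |
|---|---|---|---|---|---|
| 3 | 15% | 48 | 2.85 | 2.71 | 2.60 |
| 3 | 15% | 156 | 2.55 | 2.27 | 2.07 |
| 2 | 15% | 48 | 1.92 | 1.89 | 1.86 |
| 2 | 15% | 156 | 1.78 | 1.70 | 1.64 |
| 3 | 30% | 48 | 2.68 | 2.45 | 2.28 |
| 3 | 30% | 156 | 2.18 | 1.84 | 1.65 |

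For R = 3, d = 15% and no commercial OCA, the ratio falls by (3 − 2.85)/3 = 5% at 48 weeks and (3 − 2.55)/3 = 15% at 156 weeks. The 156-week rows are an upper end, since later enrollees are followed for less time.

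**Step 3: censoring.** Any pruritus, moderate-or-severe pruritus and severe pruritus are nested endpoints, yet the first has a different censoring date from the other two. The text does not say whether the discontinuation is of study drug or of the study. If it is of study drug, event-free patients leave the risk set on stopping, while nothing excludes a later event in a patient who has one. If it is of the study, the rule may nearly coincide with last contact and the difference is mainly wording.

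**The case against.** The strongest reply is that the closing date of a treatment-emergent window is usually set in the SAP, which is not at hand, and that the protocol forbids no later window. That has force for the definition alone. It does not reach the denominator formula or the censoring rules, which Section 15.4.4 fixes explicitly. A SAP that follows them keeps the problem; one that does not departs from the protocol.

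A second reply is that the denominator is openly labelled as time on study and matches a numerator collected over the same period, so the rate is a coherent treatment-policy summary. That stands. The fault is that it is the only rate planned and carries a treatment-emergent label.

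A reader might infer more than the documents support:

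- **That all adverse event rates are diluted.** Only pruritus and fatigue have person-time rates. The other tables are patient incidences, affected through the open window alone.
- **That rates are halved or worse.** A patient with 60 itch-days in 24 weeks on drug goes from 130 event-days per year on treatment to 65 over 48 weeks or 24 over 128 weeks. That is one patient; Step 1 gives the arm-level figures.
- **That every safety contrast shrinks.** Section 13.1.8 says drug-induced liver injury may appear or progress after the drug is stopped. Open-ended counting keeps such events in the OCA arm and may preserve a difference.
- **That 15% is a documented rate of stopping drug in each arm.** Section 15.2 uses it to size the OCA group for pharmacokinetics and does not say whether patients leave the drug or the study. Those who leave the study add no off-drug time.
- **That contamination by commercial OCA is established.** It is allowed for, but no uptake figure is given.

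**Conclusion.** The point holds as a missing on-treatment analysis, together with an inconsistent censoring rule. Following the protocol as written credits off-drug and commercial-OCA events and time to the original arm.

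For pruritus and fatigue event-day rates, the effect is dilution of the OCA–placebo contrast, provided events follow current exposure. It is modest at 48 weeks (about 8% of the OCA-arm rate with 4 of 25 stopping at Week 24), about 13% with 104 weeks off drug, and larger with commercial OCA use or more stopping. These sizes rest on assumed stopping times, uptake and rate ratios. For hepatic events the direction cannot be settled from the document. The all-study summary is legitimate and should stay; it should not stand alone.

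**What to change.** 1. Add a prespecified on-treatment analysis running from first dose to the earlier of last dose plus a justified number of days or the start of commercial OCA. The 30 days in Section 13.1.7 is no ready precedent: it is a reporting rule for serious events counted from leaving the study, not from last dose.
2. Use matching exposure time as the denominator for pruritus and fatigue event-day rates in that analysis, and state how time during dose interruptions is counted.
3. Keep the all-study-period summary alongside, with equal prominence for hepatic events of special interest so that late events stay visible. This also guards against relying only on follow-up that ends when toxicity causes stopping.
4. Use one censoring rule for all pruritus and fatigue time-to-event endpoints, saying whether discontinuation means study drug or study.

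The cost is a second set of adverse event tables and some rewording. The analysis uses data the study already collects and changes nothing in patient management.

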13.1.1.4. Adverse Events of Special Interest

The following decompensation events are adverse events of special interest; a subset of these are also captured as additional efficacy assessments (see [Section 14.2.3](#)).

- Variceal bleeding or recurrent variceal bleeding documented by endoscopy OR patient presenting with anemia or melena (hemoglobin drop ≥ 2 g/dL) and found to have varices documented by endoscopy, irrespective of hospitalization or requirement of blood transfusion.
- Gastrointestinal bleeding as a result of gastric or duodenal varices verified by endoscopy
- Hepatic encephalopathy, Grade ≥ 2
- New onset ascites requiring treatment
- Worsening of ascites (requiring increase in drug therapy or requirement of surgical procedure such as paracentesis or shunt placement)
- Refractory ascites -unresponsive to medications, and patient is not a candidate for TIPS or shunt and requires large volume paracentesis
- Hyponatremia ($\text{Na} \leq 125$ mEq/L) secondary to ascites
- Spontaneous bacterial peritonitis (confirmed by diagnostic paracentesis- by cell count/chemistry)
- Hepatorenal syndrome Type 1 and Type 2 and Acute Kidney Injury (AKI)
- Liver failure defined as worsening of liver synthetic function that is persistently worse relative to baseline and/or progressive over time:
 - Hepato-pulmonary syndrome
 - Porto-pulmonary syndrome
 - Liver Transplant
 - Increase in MELD scores by 3 points relative to baseline, persistent over time and unrelated to vitamin K deficiency related increase in INR

- Any liver related event that requires hospitalization and treatment

13.1.2. Relationship to Investigational Product

The Investigator will document her/his opinion of the relationship of the AE to treatment with the investigational product using the criteria outlined in Table 9. An AE for which there is a “reasonable possibility” that the investigational product caused the AE is otherwise referred to as suspected adverse reaction (SAR). “Reasonable possibility” means there is evidence to suggest a causal relationship between the investigational product and the AE.

If the relationship between the AE/SAE and the investigational product is determined to be “definite,” “probable,” or “possible” the event will be considered to be related to the investigational product for the purposes of expedited regulatory reporting.

Table 9: Relationship of Adverse Events to Investigational Product

Relationship	Description
Definite	A reaction that follows a reasonable temporal sequence from administration of the investigational product or in which the investigational product level has been established in body fluids or tissue; that follows a known or expected response pattern to the suspected investigational product; and that is confirmed by improvement on stopping or reducing the dosage of the investigational product, and reappearance of the reaction on repeated exposure.
Probable	A reaction that follows a reasonable temporal sequence from administration of the investigational product; that follows a known or expected response pattern to the suspected investigational product; that is confirmed by stopping or reducing the dosage of the investigational product; and that could not be reasonably explained by the known characteristics of the patient’s clinical state.
Possible	A reaction that follows a reasonable temporal sequence from administration of the investigational product; that follows a known or expected response pattern to the suspected investigational product; but that could readily be produced by a number of other factors.
Unlikely	An event that does not follow a reasonable temporal sequence from administration of the investigational product; that does not follow a known or suspected response pattern to the suspected investigational product; and that could reasonably be explained by known characteristics of the patient’s clinical state.
Not Related	Any event that does not meet the above criteria.

13.1.3. Recording Adverse Event Severity

AEs must be graded for severity (ie, intensity). A severity category of mild, moderate, or severe, as defined in Table 10, must be entered on the AE eCRF. It should be noted that the term “severe” used to grade intensity is not synonymous with the term “serious.” The assessment of severity is made regardless of investigational product relationship or of the seriousness of the AE.

Table 10: Severity of Adverse Events

Grade	Clinical Description of Severity
1 = Mild	Causing no limitation of usual activities; the patient may experience slight discomfort.
2 = Moderate	Causing some limitation of usual activities; the patient may experience annoying discomfort.
3 = Severe	Causing inability to carry out usual activities; the patient may experience intolerable discomfort or pain.

13.1.4. Reporting of Adverse Events and Serious Adverse Events

13.1.4.1. Reporting of Adverse Events

AE data will be collected from the time that signed informed consent is obtained until the patient fully completes her/his study participation.

All AEs, whether believed by the Investigator to be related or unrelated to the investigational product, must be documented in the patient's medical records, in accordance with the Investigator's normal clinical practice and on the AE eCRF. Each AE is to be evaluated for duration, intensity, frequency, seriousness, outcome, other actions taken, and relationship to the investigational product. Redacted medical record source documentation will be requested for all SAEs and emergency room visits.

In addition, the Investigator should contact the study Medical Monitor upon awareness when any signs or symptoms of hepatic decompensation are observed in any patient.

13.1.4.2. Reporting of Serious Adverse Events

In agreeing to the provisions of this protocol, the Investigator accepts all legal responsibilities for immediate reporting of SAEs to the Sponsor. Immediate reporting implies within 24 hours of becoming aware of the occurrence of an SAE.

All SAEs must be reported to the Sponsor (including suspected liver-related clinical outcome events that qualify as serious). SAEs are reported by entering the SAE data into the study specific EDC system. Entering the SAE data into the EDC system will automatically notify the Sponsor of the event. In the event that the EDC system is inaccessible, an SAE may be reported by:

- E-mail to the SAE email address: PPD [REDACTED]
- Fax using a paper SAE report form: PPD [REDACTED]

If an SAE is reported by fax, an SAE Report form must also be completed in the EDC system as soon as the EDC system is accessible. At a minimum, the following information should be provided at the time of the initial report:

- Patient number
- Event term
- At least 1 criterion classifying the event as serious

- Name and title of the reporting individual
- Causal relationship to the investigational product

The Investigator will assess whether the event is causally related to the investigational product. The Sponsor will also assess whether the event is causally related to the investigational product, in addition to assessing the overall safety profile of the investigational product. The Sponsor will notify the appropriate regulatory agencies as well as all participating Investigators of Safety Reports/Expedited Safety Reports that occur during the study within the time frames required by each regulatory agency.

Following the initial report, any additional information obtained by the Investigator about the SAE must be reported promptly to the Sponsor in the same manner as described above for the initial SAE report. Any supporting source documentation should be faxed to PPD or emailed to PPD as soon as possible.

The Investigator is responsible for submitting information on Safety Reports/Expedited Safety Reports received from the Sponsor to her/his local IRB/IEC, as directed by the local country requirements. Documentation of the submissions to IRBs/IECs must be retained in the appropriate study file(s). As instructed by the Sponsor, Safety Reports/Expedited Safety Reports should be retained in the appropriate investigative site study files or with the IB.

